2.4.1. Primary Endpoint

The primary endpoint is success at 6 months for all enrolled and implanted subjects. Success is defined as follows:

- Alive on the originally implanted device at 6 months, and the subject has not had a severe stroke; or
- Transplanted by Month 6, and the subject has not had a severe stroke prior to transplant; or
- Explanted for recovery by Month 6, and the subject has not had a severe stroke prior to explant for recovery.

All subjects with stroke events from implant to Month 6 will be required to remain in study follow-up until the post-stroke mRS measure (≥ 3 months post stroke event) is obtained, even if this occurs at the next expected follow-up visit. If a stroke subject is alive at 6 months, but dies before the post-stroke mRS is obtained, the subject will be considered a failure with regard to the primary endpoint.

A stroke is considered severe if either:

- The first mRS score assessed ≥ 3 months post stroke event is ≥ 4 ; or

- The follow-up (≥ 3 months post stroke event) mRS score is missing and the day-of-event mRS is ≥ 4 .

Specifically, any subject experiencing any of the following events will be considered a failure:

- Death by any cause prior to 183 days post-implant and prior to transplant or explant for recovery
- A severe stroke occurring prior to 183 days post-implant and prior to transplant or explant for recovery
- A stroke followed by death within 91 days post-event occurring prior to 183 days post-implant and prior to transplant or explant for recovery

Subjects with a stroke with no available mRS and no death ≥ 91 days post-stroke occurring prior to 183 days post-implant and prior to transplant or explant for recovery will be considered missing in the primary analysis.

All subjects with at least 182 days of documented follow-up without meeting any of the above failure criteria will be considered a success. Subjects not considered a success or a failure will be excluded from the analysis.

N.B. As INTERMACS only includes visits every 6 months starting at the 6 month visit, it should be noted that should a stroke occur after 3 months, a post-event mRS score may not be obtained until the 12 month visit.

Hypotheses:

$$H_0: \pi_T \leq 77.5\%$$

$$H_a: \pi_T > 77.5\%$$

where π_T = the proportion of the patient population experiencing success for the Thoracotomy group.

The success rate in this cohort will be statistically compared to the performance goal (77.5%) using an exact binomial test. Success will be met if the lower bound of the one-sided exact 95% confidence limit is greater than 77.5%.

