### 11.4 Handling of Missing Outcomes

Every effort will be made to gather all data associated with the primary, secondary and additional endpoints. A complete case analysis, which includes all subjects with complete follow up will be conducted as the primary analysis of the primary endpoint.

[REDACTED]

[REDACTED]

[REDACTED]

- [REDACTED]
- [REDACTED]
- [REDACTED]

[REDACTED]

[REDACTED]

If a subject experiences a stroke and subsequently completes the 6 month follow-up, a post-stroke (greater than 6 months post-event) mRS is still required. If the subject dies prior to the post-stroke mRS but after the 6 month follow-up, the outcome will be considered a failure.

For the secondary endpoint, imputation for missing data regarding duration of hospital stay (in days) will not be performed.

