2.1. Sample Size Estimate and Justification

2.1.1. Sample Size

Success at 6 months is estimated to be 86% compared to a performance goal of 77.5%. Using an exact binomial test, with a one-sided alpha of 0.05, and 80% Power, a sample size of 145 implanted subjects is required.

The target success estimate of 86% is based on the following:

- The primary endpoint observed in the final BTT IDE Report for the more recent BTT CAP population (N=242), resulted in a success rate of 85.8% (205 out of 239 eligible subjects) for sternotomy subjects.

- Post-approval data from the INTERMACS Registry (through Q2 2014), indicates similar results for the sternotomy population of 88.0% (396/450) with a lower rate of success for the small subset of thoracotomy (83.3%, 55/66) and thoracotomy on-pump (82.6%, 38/46) subjects.
- The INTERMACS Federal Partners Report (from Q1 2014) indicates an 85% Kaplan-Meier survival estimate at 6 months. This is not the same as “success” in that post-exchange survival is considered.

Success will be met if the lower bound of the upper one-sided exact 95% confidence interval is greater than 77.5%.

The mean length of initial hospital stay is estimated to be 26.1 days with a standard deviation of 22.8 days and a median of 20 days based on data from the BTT CAP population (N=242). Using a one sample t-test, with a one-sided alpha of 0.05, a sample of 145 implanted subjects with an average value of 21.3 days or less will result in power greater than 80%.

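### SAP 2.4.1 classifies some stroke subjects two ways in the primary endpoint: one conflict over death before the post-stroke mRS, one over a stroke with no mRS

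*SAP*

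**What the plan says.** SAP 2.4.1 handles stroke subjects in several places.

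- **Narrative:** "If a stroke subject is alive at 6 months, but dies before the post-stroke mRS is obtained, the subject will be considered a failure". Protocol 6.3 and 11.1.2 carry the same rule, and Protocol 11.4 agrees: "If the subject dies prior to the post-stroke mRS but after the 6 month follow-up, the outcome will be considered a failure". None of these sets a limit on the time from stroke to death.
- **Severe stroke:** the first mRS taken at least 3 months after the stroke is 4 or more. If that score is missing, the day-of-event mRS is 4 or more.
- **Itemised failures:** death before day 183; a severe stroke before day 183; and "A stroke followed by death within 91 days post-event occurring prior to 183 days post-implant and prior to transplant or explant for recovery".
- **Missing:** a stroke with no mRS at all and no qualifying death "will be considered missing in the primary analysis".
- **Success:** "All subjects with at least 182 days of documented follow-up without meeting any of the above failure criteria will be considered a success".
- **Timing note:** for a stroke after month 3, the follow-up mRS may come only at the 12-month visit.

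Protocol 11.4 makes the primary analysis a complete-case analysis. It also asks for an mRS more than 6 months after the event, whereas Protocol 6.3 and 11.1.2 and the SAP use at least 3 months.

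**The concern.** These sentences turn registry records into the numerator and denominator of the primary test. Two pairs of them disagree, and nothing says which takes precedence.

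First, the narrative and protocol count a death between day 91 after the stroke and the delayed mRS as a failure. The itemised list does not. Because the success rule takes in everyone who meets no failure criterion, a programmer following the list would code that subject as a success.

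Second, being missing is not a failure criterion. A stroke subject declared missing therefore also satisfies the success sentence that follows.

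The study is single-arm and open, so a choice left to programming would be made with outcomes visible.

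**Working it through.** **Design figure.** Inputs from SAP 2.1.1: "Success at 6 months is estimated to be 86% compared to a performance goal of 77.5" per cent, and "Using an exact binomial test, with a one-sided alpha of 0.05, and 80% Power, a sample size of 145 implanted subjects is required". The rule in SAP 2.4.1 is that the one-sided exact 95% lower limit exceeds 77.5%.

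- The critical count is the smallest r with P(X ≥ r | n, 0.775) ≤ 0.05. At n = 145, P(X ≥ 121) = 0.0494 and P(X ≥ 120) = 0.0752, so r = 121.
- Power is P(X ≥ 121 | 145, 0.86) = 84.3%. At n = 144 it is 79.2%, and from 145 upwards it stays at or above 80%. The planned 145 is reproduced.

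**Conflict 1, constructed subject.** Take month 6 as day 183 and month 12 as day 365. Protocol 9.2.3 gives the Month 6 visit a 60-day window either side and recommends using the later part, so it can fall as late as 183 + 60 = day 243. A stroke after 243 − 91 = day 152 cannot have a 3-month mRS by then. Let the stroke be on day 170 with day-of-event mRS 3, and death on day 270 (100 days later) with no follow-up mRS.

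| Rule | Result |
|---|---|
| SAP narrative; Protocol 6.3, 11.1.2, 11.4 | failure |
| List: death before day 183 | not met (day 270) |
| List: severe stroke | not met (follow-up mRS missing, day-of-event 3) |
| List: death within 91 days of stroke | not met (100 days) |
| 182-day sentence | success |

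For this stroke the uncovered deaths run from 170 + 92 = day 262 to day 364.

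**Conflict 2, constructed subject.** Stroke on day 60, no mRS, alive, 200 days of follow-up. The missing sentence gives missing. No failure item is met and 200 ≥ 182, so the next sentence gives success.

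**Effect on the test.** The lower limit L(x, n) solves P(X ≥ x | n, L) = 0.05, that is, L = the 5% quantile of Beta(x, n − x + 1).

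| Count | Lower limit | Goal |
|---|---|---|
| 121/145 | 77.52% | met |
| 120/145 (one moved to failure) | 76.76% | not met |
| 120/144 (one excluded) | 77.37% | not met |

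At a true rate of 86%, exactly 121 successes has probability about 6%, and 121 to 123 about 22%.

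**Effect on power.** Let k subjects be ambiguous, with 86% the rate when they count as successes.

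- As failures the rate is 0.86 − k/145. For k = 1 this is 0.8531 and power is 77.7%; k = 2 gives 70.1% and k = 3 gives 61.6%.
- Excluded, k = 1: (0.86 × 145 − 1)/144 = 0.859, with 121 still needed, and power is 78.2%.

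The range of k is an assumption.

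**Scale.** Protocol 4.2.3 reports 10 ischemic and 4 hemorrhagic strokes by day 180 in 140 HVAD subjects. These are events, 9 in days 0–30 and 5 in days 31–180. A stroke by day 30 reaches 91 days by day 121, before the earliest Month 6 visit (183 − 60 = day 123). Conflict 1 therefore concerns mainly later strokes, and only those followed by a death in the gap or a missed mRS.

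**The case against.** The best defence of the SAP on conflict 1 is that the narrative stands above the success sentence and can itself be read as one of the failure criteria referred to. The list gives sufficient conditions and never says they are the only ones. On that reading the day-270 death is a failure everywhere. This is tenable, but it leaves the 91-day limit with no function, and the list is presented as the specific form of the definition.

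On conflict 2, the missing sentence is the more specific and fits Protocol 11.4's complete-case rule, so missing is probably what was intended. The success sentence still says all subjects and has no exception.

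The Month 6 window also matters. For a stroke around day 150, a visit near day 243 could supply a qualifying mRS (243 − 150 = 93 days), which narrows the gap without closing it.

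A reader might infer that both conflicts favour the device. That holds only for conflict 1, where the list departs from the protocol towards success. In conflict 2, missing is less favourable than success (120/144 fails where 121/145 passes). The SAP also counts a day-of-event mRS of 4 or more as severe when the later score is missing, which is conservative.

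**Conclusion.** The rules are inconsistent as written, and a literal programmer can misclassify a subject in the primary endpoint. Conflict 1 is failure against success; conflict 2 is missing against success. Both rest on visible text and not on the blacked-out parts of Protocol 11.4 or SAP 2.4.7.

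A reader might go further and say that one subject can hold all three statuses. The literal text does not establish this. It would also require reading the day-183 limit in the missing rule as applying to the death and not to the stroke; that attachment is unclear and should be settled.

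The number of subjects affected cannot be derived from the documents. It is likely to be small, since each case needs a stroke plus either a death in a narrow window or a wholly absent mRS. One subject reverses the conclusion only near the boundary, and the critical count of 121 applies at n = 145; the protocol allows enrolment above that.

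**What to change.** In SAP 2.4.1:

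1. Replace the 91-day item with: stroke before day 183 and before transplant or explant for recovery, followed by death before the first mRS at least 3 months post-stroke is obtained, is a failure.
2. State that the day-183 limit in that item and in the missing rule refers to the stroke.
3. Limit the 182-day success sentence to subjects with no stroke, or with a stroke classified as not severe. Strokes with no mRS then remain missing, in line with Protocol 11.4's complete-case primary analysis.
4. Show those missing subjects as failures in a sensitivity analysis, unless the redacted text already does so. Making them failures in the primary analysis would be stricter but would depart from Protocol 11.4, so it is a trade-off and not a correction.

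In Protocol 11.4, reconcile the mRS timing of more than 6 months with the at-least-3-months definition used elsewhere.

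The cost is wording only: no new data and no change in sample size. The success count may be slightly lower. Like the narrative and protocol rules, item 1 has no end date, so a missed mRS followed by a much later death would still be a 6-month failure. If a cut-off is wanted, both documents should state it.

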### 7.2 Subject Participation and Study Duration

All subjects will be followed for the primary endpoint, and at subsequent follow-up visits, according to the approved INTERMACS® protocol and using data from INTERMACS®.

Data collection for analysis and subject status for inclusion in analyses will be assessed as follows:

- Subjects who have been transplanted prior to month 6 post implant will be considered complete at the time of the primary endpoint visit time-point.
- Subjects, who have a device exchange prior to month 6, will be evaluated according to the original implant date.

- Subjects who remain on device support after the primary endpoint time-point, either the original device or exchange device, will be followed according to the INTERMACS® protocol until transplant, or until 2.5 years post implant of the original device. A subject's study participation is considered complete at either the time of at induction of anesthesia for transplant, or at the 2.5 year post implant visit.
- Subjects who have been explanted for recovery prior to month 6 will be followed until their next scheduled follow-up visit according to the INTERMACS® protocol, at which time their participation in the study is considered complete.
- The per-protocol analysis population will include those thoracotomy subjects with the outflow in the ascending aorta only. As a result, enrollment may exceed sample size requirements.
- The per-protocol analysis population will include those thoracotomy subjects with the procedure performed on-pump only. As a result, enrollment may exceed sample size requirements.

Subject data will be evaluated for a maximum of 2.5 years.

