#### 11.1.2 Primary Endpoint

The primary endpoint is success at 6 months defined as all enrolled and implanted subjects:

- Alive on the originally implanted device at 6 months, and the subject has not had a stroke with a modified Rankin Scale  $\geq 4$  (assessed  $\geq 3$  months post stroke event); or
- Transplanted by Month 6, and the subject has not had a stroke with a modified Rankin Scale  $\geq 4$  (assessed  $\geq 3$  months post stroke event), or
- Explanted for recovery by Month 6, and the subject has not had a stroke with a modified Rankin Scale  $\geq 4$  (assessed  $\geq 3$  months post stroke event).

All subjects with stroke events from implant to Month 6 will be required to remain in follow-up until the post-stroke mRS measure ( $\geq 3$  months post stroke event) is obtained, even if this occurs after the 6-month visit. If a stroke subject is alive at 6 months, but dies before the post-stroke mRS is obtained, the subject will be considered a failure with regard to the primary endpoint.

Hypothesis:

$$H_0: \pi_T \leq 77.5\%$$

$$H_a: \pi_T > 77.5\%$$

$\pi_T$  = the expected proportion of subjects experiencing success for the Thoracotomy group

The success prevalence in the thoracotomy group will be statistically compared to the performance goal (77.5%) using an exact binomial test (i.e., the lower 95% one-sided confidence limit will be greater than 77.5%). Success will be met if the lower bound of the one-sided exact 95% confidence limit is greater than 77.5%.

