The Intent-to-Treat (ITT) subject population will include all enrolled subjects intended to receive the HVAD® pump via thoracotomy at the time of skin incision.

The Per-Protocol (PP) subject population will include all ITT subjects who were implanted with the HVAD pump® via thoracotomy, on-pump, and with outflow to the ascending aorta. Sample size requirements reflect the minimum number of subjects needed for the PP population.

Data recorded in the INTERMACS® database to the primary endpoint at 6 months post implant of the HeartWare® HVAD will be evaluated.

Subjects who remain on device support after the primary endpoint time-point, either the original device or exchange device, will be followed according to the INTERMACS® protocol until transplant, or until 5 years post implant of the original device. A subject's study participation is considered complete at either the time of induction of anesthesia for transplant, or at the 5 year post implant visit.

- Subjects who have been explanted for recovery prior to month 6 will be followed until their next scheduled follow-up visit according to the INTERMACS® protocol, at which time their participation in the study is considered complete.
- The per-protocol analysis population will include those thoracotomy subjects with the outflow in the ascending aorta only as well as those thoracotomy subjects with the procedure performed on-pump only. As a result, enrollment may exceed sample size requirements.

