2.4.3. Other Endpoints

Additional endpoints in this study include:

1. Success at 6 months defined as alive on original device or transplanted or explanted for recovery by month 6.
2. Overall Survival on HVAD (Time to Death on original device).

3. Frequency and rates of adverse events per INTERMACS® definition throughout original VAD support.
4. Time on Cardiac Pulmonary Bypass.
5. Perioperative Bleeding and Transfusions (within 48 hours post-op).
6. Length of initial ICU stay.
7. Prevalence and causes of re-hospitalizations (within 6 month period following implantation).
8. Health Status improvement at 6 month, as measured by KCCQ and EuroQol EQ-5D.
9. Functional status improvement, as measured by NYHA and 6-minute walk.
10. Success at 6 months (defined like the primary endpoint) for those screen failures who undergo thoracotomy.

Additional endpoints include observed and change in laboratory, hemodynamics and echocardiogram parameters and neurocognitive testing scores at 6 months. Additional observational endpoints will also be assessed at 6 months. The additional endpoints will be analyzed descriptively, i.e., no inferential analysis will be performed and conclusions will be formulated with caution as these endpoints are not powered.

Time-to-event outcomes will be presented using Kaplan-Meier curves. Quantitative outcomes will be summarized and the corresponding 95% confidence intervals will be derived.

Categorical outcomes will be summarized by presenting frequency and percentage results as well as the corresponding 95% confidence intervals. In particular, adverse events and stroke events summaries will be presented by calculating prevalence (frequency) and event rates (events per patient-year).

Strokes are neurological events specified as an ICVA or an HCVA, as per the current INTERMACS event definition (See Appendix D of the protocol).

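### The operational success rule in SAP 2.4.1 omits device exchange, so a subject alive on an exchanged pump is coded a success or excluded, although the endpoint definition makes that subject a failure

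*SAP*

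**What the plan says.** SAP 2.4.1 opens with a three-part definition of success. The part for subjects still on support is "Alive on the originally implanted device at 6 months, and the subject has not had a severe stroke". The other two parts cover transplant and explant for recovery by Month 6, again without severe stroke. Protocol 6.3 and 11.1.2 make the same demand: "Alive on the originally implanted device at 6 months".

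The section then turns to operational rules and lists three failure events: death before day 183, severe stroke before day 183, and a stroke in that period followed by death within 91 days. Each counts only if it comes before transplant or explant for recovery. Exchange is not listed. Nor is explant or shutting off the pump for a reason other than recovery or transplant. Two sentences settle everyone else: "All subjects with at least 182 days of documented follow-up without meeting any of the above failure criteria will be considered a success", and "Subjects not considered a success or a failure will be excluded from the analysis".

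Exchanged subjects are not dropped from the study. Protocol 7.2 says: "Subjects, who have a device exchange prior to month 6, will be evaluated according to the original implant date". SAP 1.2 says that subjects on support after the 6-month time-point, "either the original device or exchange device, will be followed according to the INTERMACS" protocol.

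Two other places show what was meant. SAP 2.1.1 says the registry survival figure differs from success "in that post-exchange survival is considered". SAP 2.4.3 gives as an additional endpoint: "Success at 6 months defined as alive on original device or transplanted or explanted for recovery by month 6".

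**The concern.** One section gives two classifications for the same subject. Under the definition, a subject alive at 6 months on a replacement pump has failed. Under the operational rules, that subject has no failure event and, with 182 days of follow-up, is a success. Someone programming the endpoint would naturally code the operational rules, because they carry the day counts and the stroke logic.

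What counts as documented follow-up after an exchange is also undefined. SAP 3.2 stops patient-time at exchange, though only for adverse event rates. If that cut-off were borrowed, a subject exchanged before day 182 would be neither a success nor a failure and would leave the denominator.

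Both departures favour the device. The trial has one arm and a fixed goal of 77.5%, so no control group shares the misclassification, and a handful of subjects can decide the result.

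**Working it through.** **1. The planned test.** Inputs from SAP 2.1.1 and 2.4.1: n = 145, goal p0 = 0.775, expected rate 0.86, exact binomial test, one-sided alpha 0.05. The critical count is the smallest r with P(X ≥ r | 145, 0.775) ≤ 0.05.

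- r = 121 (121/145 = 83.4%).
- Size: P(X ≥ 121 | 145, 0.775) = 0.0494.
- Power: P(X ≥ 121 | 145, 0.86) = 0.843.
- Exact one-sided 95% lower bounds: 121/145 gives 77.52% (passes); 120/145 gives 76.76% (fails).

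Power moves in a saw-tooth as n grows. It is 79.2% at n = 144, and from n = 145 it stays at or above 80% (checked to n = 249). The planned 145 is therefore reproduced.

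**2. One subject under each rule.** Take a subject exchanged at, say, day 90, with no stroke, alive on the new pump at day 182.

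| Rule applied | Result |
|---|---|
| Definition (SAP 2.4.1; protocol 6.3, 11.1.2) | Failure: not on the original device |
| Operational list, follow-up continuing past exchange | Success |
| Definition blocks success, then the residual rule | Excluded |
| Follow-up taken to end at exchange, then the residual rule | Excluded |

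**3. Effect on the chance of passing.** Let q be the share of subjects alive after exchange with no listed failure event, and hold the definition-based success rate at exactly 0.775. The documents give no q for this trial. Protocol 4.2.3 reports 5/140 = 3.6% alive after exchange at day 180 in the earlier sternotomy trial, without their stroke status.

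- Coded as success: P(X ≥ 121 | 145, 0.775 + q).
- Excluded: K ~ Bin(145, q) subjects are removed, n becomes 145 − K, the success rate becomes 0.775/(1 − q), the critical count is recomputed for each n, and the result is averaged over K.

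| q | Coded as success | Excluded |
|---|---|---|
| 0 (definition followed) | 0.049 | 0.049 |
| 1/145 (one expected subject) | 0.073 | 0.056 |
| 1% | 0.086 | 0.063 |
| 2% | 0.140 | 0.097 |
| 3% | 0.217 | 0.144 |
| 5/140 = 3.6% | 0.271 | 0.177 |
| 5% | 0.433 | 0.280 |

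The exclusion column depends somewhat on the model. Fixing the number excluded at its rounded expected value, instead of averaging, gives 0.054, 0.098, 0.200 and 0.265 at 1%, 2%, 3.6% and 5%.

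**4. Worked data with five exchange survivors among 145.**

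- 116 successes by the definition: 116/145, lower bound 73.7%, fails. Coded as successes: 116 + 5 = 121, 121/145, lower bound 77.52%, passes.
- 117 successes by the definition: 117/145, lower bound 74.5%, fails. Excluded: 145 − 5 = 140, 117/140, lower bound 77.54%, passes.

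**The case against.** The best defence is that the intent is plain. The original-device condition appears wherever the primary endpoint is defined, and SAP 2.1.1 separates success from post-exchange survival. The definition comes first, and the list says that subjects with the named events fail, not that only they fail. A careful analyst could read the list as adding day counts and stroke rules to the definition. That reading is reasonable and probably the one intended. It does not remove the conflict, because the success sentence covers all subjects without a listed event and the SAP does not say which rule takes precedence.

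The size can also be questioned. The probabilities are computed at the boundary of the null, the exchange rates are assumed, and the worked counts sit at the critical value. With five survivors coded as successes, the conclusion changes only for definition-based counts of 116 to 120; at the planned 86% rate the chance of landing there is about 14%. This is fair context. Type I error is nevertheless defined at the boundary, and that is where the rule loses control.

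The cut-off in SAP 3.2 is written for adverse event rates, so carrying it into the endpoint is conjecture. Exclusion does not depend on it, since the definition combined with the residual rule gives the same result.

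Parts of protocol 11.4 and SAP 2.4.7 are redacted and might mention exchange. SAP 2.4.1 is shown in full, and its classification rule points to no other section.

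**Conclusion.** The concern holds. For a subject alive on an exchanged pump without a listed event, SAP 2.4.1 contradicts itself: the definition gives failure, and the operational rules give success or exclusion. The textual conflict does not depend on any assumed rate.

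The size does. It assumes that the operational rules are applied as written, that the true definition-based rate is 77.5%, and that 1% to 5% of subjects are alive after exchange. Under those conditions the nominal 5% test passes 8.6% to 43.3% of the time if these subjects are coded successes, and 6.3% to 28.0% if they are excluded. Even one expected subject in 145 takes it to 7.3% or 5.6%. Exchanged subjects who die or have a severe stroke before day 183 remain failures under either rule and do not contribute. Because this is the primary endpoint's classification rule, it should be corrected before analysis.

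**What to change.** 1. Add a failure event to the list in SAP 2.4.1: *exchange of the original pump, or its explant or deactivation for any reason other than recovery or transplant, before day 183 and before any transplant or explant for recovery*.

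2. Replace the success sentence with three branches: *(a) alive on the original pump with 182 or more days of documented follow-up and no failure event; (b) transplanted by Month 6 with no earlier failure event; (c) explanted for recovery by Month 6 with no earlier failure event*. Keep the existing rule for missing mRS. A single requirement of 182 days on the original pump would not do, because it would drop subjects transplanted or recovered earlier, who are successes by definition. In the earlier trial 37/140 were alive post-transplant at day 180 (protocol 4.2.3).

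3. State how exchange followed by transplant or explant for recovery by Month 6 is classified, since those two parts of the definition do not mention the original pump. If it is a failure, keep item 1 as worded and add the original-pump condition to both parts. If it is a success, limit item 1 to exchanges not followed by transplant or explant for recovery by Month 6, and make the branches in item 2 match.

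The cost is a few lines of SAP text. SAP 3.2 already derives days to exchange, explant and transplant; it has no separate day count for deactivation, which appears only in the adverse event rate rule. With exchange counted as failure, the planned test stands: 121/145 needed, size 0.049, power 0.843 at 86%, n unchanged. The observed success rate may come out slightly lower.

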#### 9.2.3 Follow-up Assessments

Follow-up visit time-points specified in the INTERMACS® protocol include: At discharge, 1 week, 1 month, 3 months, 6 months and every 6 months until outcome/ 2.5 years.

At discharge assessments recorded in the INTERMACS® database include: adverse events and discharge date.

Assessments at one week and one month include: hemodynamics, laboratory values, medications, echocardiogram, medical condition as described by NYHA class and adverse events.

Assessments at 3 and 6 months, and then every 6 months until outcome / 2.5 years include: laboratory values, medications, hemodynamics, echocardiogram, medical condition as described by NYHA class and INTERMACS® patient status, neurocognitive testing, quality of life testing, exercise function and adverse events.

Every attempt should be made to perform evaluations at the designated time points. Visits and associated visit windows will be as per the INTERMACS protocol and procedures. While per the INTERMACS protocol, the Month 6 visit has a  $\pm 60$  day window, it is recommended that the Primary Endpoint visit occur at Month 6 + 60 days, whenever possible.

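### Event-free subjects seen early in the Month 6 window can drop out of the primary analysis under the SAP's 182-day rule, while recorded deaths and severe strokes before day 183 stay in

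*SAP*

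**What the plan says.** Protocol 9.2.3 takes its visit windows from the registry. It states a window of ±60 days for Month 6 and adds that "it is recommended that the Primary Endpoint visit occur at Month 6 + 60 days, whenever possible". That is a recommendation. A visit from about day 123 (183 − 60) is in window.

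Protocol 11.4 sets the approach to missing outcomes: "A complete case analysis, which includes all subjects with complete follow up will be conducted as the primary analysis of the primary endpoint".

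SAP 2.4.1 supplies the working rules:

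- Success: "All subjects with at least 182 days of documented follow-up without meeting any of the above failure criteria will be considered a success".
- Failure: the list includes "Death by any cause prior to 183 days post-implant and prior to transplant or explant for recovery" and a severe stroke in the same period. Neither needs a minimum length of follow-up.
- Everyone else: "Subjects not considered a success or a failure will be excluded from the analysis".
- A stroke with no usable mRS and no qualifying death "will be considered missing in the primary analysis".

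SAP 2.5 refers to an initial results report at a data cut, followed by a final report. No readable section dates that cut or links it to the close of the Month 6 window.

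**The concern.** The visit rule and the classification rule do not fit together. Take a subject on the original device who attends at day 150 and is well. The Month 6 visit is valid, but only 150 days are documented. The next scheduled visit is Month 12. If nothing later is on file at the primary data cut, the subject is neither success nor failure and is removed. Had the same subject died on day 160 and the death been recorded, the subject would count as a failure. The registry protocol (A.4.3) says crucial events are submitted as they occur, while event-free status is confirmed at scheduled visits.

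Whether a subject enters the denominator then depends partly on the outcome. Taken alone, this mechanism removes successes and keeps recorded failures. The estimated success rate is pulled down, the evaluable number falls below 145, and the planned power is not delivered. Subjects transplanted before Month 6 are not the issue here, because the SAP's definition counts them as successes without waiting for day 182.

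**Working it through.** **Inputs.** From SAP 2.1.1: expected success 86%, performance goal 77.5%, exact binomial test, one-sided alpha 0.05, 80% power, N = 145. From Protocol 4.2.3: in the earlier US trial, 127 of 140 were successes and 88 of 140 were alive on the original device at day 180. From Protocol 6.2: planned enrolment from the fourth quarter of 2014 to the first quarter of 2016, about 18 months. The share of event-free subjects with no record from day 182 on is not in the documents, so a range is assumed.

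**Reproducing the plan.** At N = 145 the exact test needs at least 121 successes (one-sided lower limit for 121/145 is 77.52%; for 120/145 it is 76.76%). Exact alpha is 0.0494 and power at 86% is 0.843. Power at N = 144 is 0.792. The planned 145 is confirmed, and it sits on a local peak of the exact test's saw-toothed power curve.

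**Effect of dropping event-free subjects only.** Let successes X ~ Bin(145, p). Each success is excluded with probability f, every failure is kept, and the exact test is re-applied at the reduced N. The expected observed rate is p(1 − f) / [p(1 − f) + (1 − p)]. For example, at f = 0.05: 0.817 / (0.817 + 0.14) = 85.4%. The mean N is 145(1 − pf). Power is at p = 0.86 and type I error at p = 0.775.

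| f (assumed, all event-free subjects) | Expected rate | Mean N | Power | Type I error |
|---|---|---|---|---|
| 0 | 86.0% | 145 | 0.843 | 0.049 |
| 1% | 85.9% | 144 | 0.800 | 0.037 |
| 2% | 85.8% | 143 | 0.784 | 0.032 |
| 5% | 85.4% | 139 | 0.736 | 0.024 |
| 10% | 84.7% | 133 | 0.632 | 0.012 |

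Part of the loss is simply a smaller N. If the same share were lost regardless of outcome, power would be 0.80 at 5% and 0.77 at 10%. The remainder comes from the dependence on outcome.

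**Restricting the loss to those exposed.** Only subjects still on the device can be caught. In the earlier trial that was 88/127 = 69% of successes. If 5%, 10% or 15% of on-device event-free subjects are lost, f is 3.5%, 6.9% or 10.4% and power is 0.76, 0.70 or 0.62.

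Anyone with a Month 12 record by the cut is also safe. Assume even accrual over 18 months and a cut 6 months after the last implant. Then about 6/18 = one third have not reached Month 12, f is 1.2%, 2.3% or 3.5%, and power is 0.80, 0.78 or 0.76.

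**How close a result must be.** A result near the planning value, 125/145 (lower limit 80.6%), still passes after 20 event-free exclusions (105/125, 77.6%) and fails at the 21st (104/124, 77.4%). A result of 122/145 (78.3%) fails after six (116/139, 77.4%).

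**The case against.** The strongest reply is that an early visit by itself drops nobody. SAP 2.4.1 asks for documented follow-up, not for a visit on or after day 182. Protocol 7.2 keeps on-device subjects in follow-up to transplant or 2.5 years, and re-hospitalizations and events are recorded between visits. A later record can supply day 182. No early cut is written down, and SAP 2.4.1 expects some post-stroke mRS scores to arrive as late as Month 12. All of this stands, and it narrows the exposure to subjects with an early visit and nothing later on file at the cut. It does not close the gap: the cut is undated, no sentence says that a later contact may establish day-182 status, and a subject lost after an early visit is never recovered.

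A reader might also infer that every failure is retained. The documents do not support that. A stroke with no mRS is set to missing, and a death after the last contact may go unrecorded. Device exchange is also absent from the SAP's list of failure events, although success on support requires the original device; read literally, that could act upwards. The table models none of these, so it shows the effect of one mechanism and not the net bias.

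The recommendation in Protocol 9.2.3 lowers the number of early visits but does not exclude them. Parts of Protocol 11.4 and SAP 2.4.7 are redacted, and a missing-data sensitivity analysis may sit there. It would not change the primary rule in SAP 2.4.1.

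**Conclusion.** The mismatch is real and comes from stated rules. An event-free, on-device subject seen in window before day 182, with no later record at the cut, is excluded; a recorded death or severe stroke before day 183 is not. This mechanism lowers the complete-case success rate and erodes power.

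Its size rests on an assumed share. A loss of 1% of all event-free subjects already takes power to the planned 80%, and 5% takes it to about 0.74. If the loss is confined to on-device subjects not yet at Month 12, power is about 0.76 to 0.80 for losses of 5% to 15%; that range also assumes the earlier trial's device share, even accrual and a cut at 6 months.

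A reader might infer that the rule could produce a false claim of success. It does not: under this mechanism type I error falls from 0.049 to 0.024 at 5% loss and 0.012 at 10%. What is at risk is the accuracy of the estimate and the chance of meeting the goal when the true rate is 86%. Nor does a result near the plan turn on a handful of exclusions; only a result close to the pass mark does.

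**What to change.** **SAP 2.4.1.** State that day-182 status (alive, original device, no severe stroke) is established from any dated registry record or contact on or after day 182, including later visits. Set the primary data cut no earlier than the last implant + 243 days (183 + 60). This is a floor, since some post-stroke mRS scores may come later.

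**Protocol 9.2.3.** Make the primary endpoint visit Month 6 −0/+60 days. Alternatively, for a subject seen earlier, obtain a dated chart-based status on or after day 183. A chart check stays close to Protocol 9.2, which requires no study-specific procedures beyond consent. The cut date alone would not rescue a subject seen at day 150 whose next visit is Month 12, so one of these two steps is needed as well.

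**Sensitivity analysis.** Count subjects last seen event-free within the window but before day 182 first as successes, then as failures, and report both beside the primary result.

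**Cost.** A few sentences, a few chart checks and up to about 60 days' delay to the cut.
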